10.6.2.1. Handling of Missing Dates

Element	Reporting Detail
General	
 Partial dates will be displayed as captured in subject listing displays.
Adverse Events	
 The eCRF allows for the possibility of partial dates (i.e., only month and year) to be recorded for AE start and end dates; that is, the day of the month may be missing. In such a case, the following conventions will be applied for calculating the time to onset and the duration of the event: 
 Missing Start Day: First of the month will be used unless this is before the start date of study treatment; in this case the study treatment start date will be used and hence the event is considered On-treatment as per Appendix 4: Study Phases and Treatment Emergent Adverse Events. Missing Stop Day: Last day of the month will be used, unless this is after the stop date of study treatment; in this case the study treatment stop date will be used. Completely missing start or end dates will remain missing, with no imputation applied. Consequently, time to onset and duration of such events will be missing.

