2.3. Study Design

Design Features	
 This is a single dose, open-label study in adult Japanese healthy participants to evaluate the PK, safety and tolerability of DTG/RPV 50 mg/25 mg FDC tablets. The study will consist of screening, treatment and follow-up phases.
Dosing	
 Enrolled participants will receive the DTG/RPV 50 mg/25 mg FDC tablet as a single oral dose in a fed state.
Time & Events	
 Refer to Appendix 2: Schedule of Activities
Treatment Assignment	
 A maximum of 16 healthy adult Japanese subjects will be randomized such that a minimum of approximately 13 evaluable subjects complete the study with at least 3 participants of each gender enrolled.
Interim Analysis	
 There will be no interim analysis.

See study protocol for further details

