10.3.2. Study Phases for AE Data

Assessments and events will be classified according to time of occurrence relative to the start and/or stop date of the study treatment.

Study Phase	Definition
Pre-Treatment	Event Start Date < Initial Study Treatment Date
On-Treatment	If event onset date is on or after the initial treatment date & on or before the final treatment date with 3 days lag time. Initial Study Treatment Date ≤ Event Start Date ≤ Final Study Treatment Date + 3 days
Post-Treatment	If event onset date is after the final treatment date with 3 days lag time. Event Start Date > Final Study Treatment Date + 3 days
Onset Time Since 1 st Dose (Days)	If Treatment Date > Event Onset Date = Event Onset Date – Treatment Date If Treatment Date ≤ Event Onset Date = Event Onset Date – Treatment Date+1 Missing otherwise.
Duration (Days)	Event Resolution Date – Event Onset Date + 1
Drug-related	If relationship is marked 'YES' on eCRF OR value is missing.

NOTES:

- If the initial and final study treatment dates are missing then the event will be considered to be On-Treatment.

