10.6.2.2. Handling of Partial Dates

Element	Reporting Detail
Concomitant Medications	
 Partial dates for any concomitant medications recorded in the eCRF will be imputed using the following convention:

	
• If the partial date is a start date, a '01' will be used for the day and 'Jan' will be used for the month• If the partial date is a stop date, a '28/29/30/31' will be used for the day (dependent on the month and year) and 'Dec' will be used for the month.• The recorded partial date will be displayed in listings.
AEs	
• Any partial dates for AEs will be raised to data management. If the full date cannot be ascertained, the following assumptions will be made:
○ If the partial date is a start date, a '01' will be used for the day and 'Jan' will be used for the month.○ However, if these results in a date prior to Week 1 Day 1 and the event could possibly have occurred during treatment from the partial information, then the Week 1 Day 1 date will be assumed to be the start date.○ The AE will then be considered to start on-treatment (worst case).○ If the partial date is a stop date, a '28/29/30/31' will be used for the day (dependent on the month and year) and 'Dec' will be used for the month.• The recorded partial date will be displayed in listings.

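### SAP 10.6.2.1 caps a missing adverse-event stop day at the treatment stop date, here the single dosing day, so derived durations become 1 − k days for an onset k days after dosing

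*SAP*

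**What the plan says.** SAP 10.6.2.1 deals with AE dates recorded as month and year only. It says that "the following conventions will be applied for calculating the time to onset and the duration of the event". A missing stop day becomes the last day of the month, "unless this is after the stop date of study treatment; in this case the study treatment stop date will be used". Completely missing dates are not imputed.

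SAP 10.3.2 defines AE duration as "Event Resolution Date – Event Onset Date + 1". It also defines a Post-Treatment phase: "If event onset date is after the final treatment date with 3 days lag time".

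SAP 2.3 gives the dosing: "Enrolled participants will receive the DTG/RPV 50 mg/25 mg FDC tablet as a single oral dose in a fed state". Under Protocol 8.3.1, AEs are collected from dosing to the follow-up visit, which Protocol 4.1 places 12 to 17 days after the dose.

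SAP 10.6.2.2 has a second entry for AEs. It begins "Any partial dates for AEs will be raised to data management" and then gives assumptions for dates that cannot be completed. For a stop date, a month-end day "will be used for the day (dependent on the month and year) and 'Dec' will be used for the month". This entry has no cap at treatment stop, and nothing in either section says which of them takes precedence.

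**The concern.** Capping an AE's end at treatment stop can be workable where treatment lasts for weeks. Here treatment lasts one day and AE collection continues for up to 17 days after it. The cap therefore ends the event on a day that precedes the onset of every AE that starts after the dosing day.

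Duration is a prespecified derived variable, and the written rule gives it impossible values. Because a second section covers the same kind of date without the cap, two programmers could each follow the SAP and derive different durations for one event. Or a programmer could notice the negative value and work around it without documentation.

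**Working it through.** The plan states no figure on this point, so there is none to reproduce. The check is date arithmetic.

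**Inputs**
- One dose, on day D (SAP 2.3). The SAP gives no other definition of the treatment stop date, so I take it as D.
- Imputed stop under SAP 10.6.2.1 = the earlier of month-end and D.
- Duration = stop − onset + 1 (SAP 10.3.2).
- Onset = D + k, with k from 0 to 17 (Protocol 8.3.1 and 4.1).

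**Step 1: the imputed stop date.** For an AE that truly ends on or after D, the last day of its stop month is also on or after D. The earlier of the two dates is therefore always D. An enumeration over every dosing date in an assumed 365-day year, every onset from D to D + 17 and every stop from onset to D + 17 covers 365 × (18 × 19 / 2) = 365 × 171 = 62,415 combinations. All return D.

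**Step 2: the duration.** D − (D + k) + 1 = 1 − k.

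| Onset, days after dose (k) | Duration, days |
|---|---|
| 0 | 1 |
| 1 | 0 |
| 4 | −3 |
| 11 | −10 |
| 17 | −16 |

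At k = 0 the value is possible but is fixed at 1 day whatever the true length. An onset more than 3 days after the dose is one that SAP 10.3.2 itself classes as Post-Treatment, so such an AE with a missing stop day gets −3 days or less.

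**Step 3: the two sections side by side.** Illustrative dates: dose 6 May, onset 10 May, stop recorded as 'May'.
- SAP 10.6.2.1: stop 6 May; 6 − 10 + 1 = −3 days.
- SAP 10.6.2.2 with the recorded month kept: stop 31 May; 31 − 10 + 1 = 22 days.

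**Step 4: could the sections serve different purposes?** SAP 10.6.2.1 names time to onset and duration as its purpose. Phase under SAP 10.3.2 depends on the event start date only, so the stop-date rule in 10.6.2.2 has no stated use other than duration. The two rules address the same quantity.

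**Step 5: does the 3-day lag help?** SAP 10.3.1 and 10.3.2 add the lag to the treatment date separately, and 10.6.2.1 does not include it. If it were included and month-end fell later, duration would be (D + 3) − (D + k) + 1 = 4 − k: 0 at k = 4 and −13 at k = 17. The defect would only move.

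**The case against.** The best case on the other side is about reach, and most of it stands.

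- **Few events can be affected.** At most 16 participants are enrolled. They stay in the unit from Day −1 to Day 3, then attend on Days 4, 6, 8, 10 and 12, with AE review throughout. Partial AE dates are queried before any imputation. This makes a residual partial date unlikely, but the imputation rules exist for exactly the cases that survive the query.
- **No listed table depends on it.** AE Tables 3.1 to 3.3 summarise by system organ class and preferred term, drug-relatedness and maximum grade. Listings show the recorded partial date. Whether a listing shell prints a derived duration cannot be seen from the SAP.
- **The large negative values are remote.** An onset at k = 17 falls on the last possible follow-up day. An AE still ongoing then may have no stop date at all, and completely missing dates are left missing.

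Two stronger readings are tempting and should not be made.

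- A reader might take the December wording in 10.6.2.2 literally and conclude that a stop recorded as 'May' is moved to year-end. The same sentence makes the day depend on the month and year. If December always replaced the month, the day would always be 31 and that clause would do nothing. The natural reading keeps a recorded month and uses December only when the month is missing too.
- A reader might infer a general conflict between the start-date rules, because 10.6.2.2 says "If the partial date is a start date, a '01' will be used for the day and 'Jan' will be used for the month". With a recorded month kept, both sections use the first of that month. For AEs that begin on or after dosing, both move an earlier date up to dosing day. The floor in 10.6.2.2 applies only if the event could have occurred during treatment, so it cannot pull an onset in a clearly later month back to the dosing day.

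What survives is the stop-day cap, and the absence of any stated precedence between the two sections.

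**Conclusion.** The point holds as a minor error in the SAP text. As written, 10.6.2.1 returns a duration of 1 − k days for any AE that ends on or after dosing and has a stop month but no stop day. That is zero or negative for every onset after the dosing day. SAP 10.6.2.2 gives a different stop date for the same record, and the SAP does not say which to use.

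The effect is confined to derived durations of AEs that remain partially dated after query. The documents give no basis for estimating how many there will be, and there may be none. AE counts, grades and the PK endpoints are unaffected, so nothing here supports an inference that the safety tables or the primary analysis are unreliable.

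The conclusion assumes that the treatment stop date is the single dosing day. It leaves aside one narrow case: a study-related SAE recorded between consent and dosing that ends in a month before dosing, where month-end falls before the cap.

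**What to change.** 1. In SAP 10.6.2.1, delete the cap at treatment stop. Impute a missing stop day as the last day of the recorded month, and never earlier than the onset date.
2. As an option, also bound the imputed date at last study contact, including any extended follow-up under Protocol 8.3.3. In the May example the follow-up visit falls between 17 May (Day 12, allowed by footnote 3 of the Schedule of Activities) and 23 May (17 days after the dose). If that visit is the last contact, the duration is 17 − 10 + 1 = 8 to 23 − 10 + 1 = 14 days, against 22 without the bound. Either convention removes the impossible values.
3. State that 10.6.2.1 governs when only the day is missing, and that the January and December wording in 10.6.2.2 applies only when the month is missing as well.
4. Keep the data-management query as the first step.

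The cost is SAP wording. No data collection, visit or planned display changes.

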10.6.2.2. Handling of Partial Dates

Element	Reporting Detail
Concomitant Medications	
 Partial dates for any concomitant medications recorded in the eCRF will be imputed using the following convention:

	
• If the partial date is a start date, a '01' will be used for the day and 'Jan' will be used for the month• If the partial date is a stop date, a '28/29/30/31' will be used for the day (dependent on the month and year) and 'Dec' will be used for the month.• The recorded partial date will be displayed in listings.
AEs	
• Any partial dates for AEs will be raised to data management. If the full date cannot be ascertained, the following assumptions will be made:
○ If the partial date is a start date, a '01' will be used for the day and 'Jan' will be used for the month.○ However, if these results in a date prior to Week 1 Day 1 and the event could possibly have occurred during treatment from the partial information, then the Week 1 Day 1 date will be assumed to be the start date.○ The AE will then be considered to start on-treatment (worst case).○ If the partial date is a stop date, a '28/29/30/31' will be used for the day (dependent on the month and year) and 'Dec' will be used for the month.• The recorded partial date will be displayed in listings.

10.7. Appendix 7: Values of Potential Clinical Importance

10.7.1. Laboratory Values

10.7.2. ECG

ECG Parameter	Units	Clinical Concern Range	
		Lower	Upper
Absolute			
Absolute QTc Interval	msec		> 450 ^[1]
Absolute PR Interval	msec	< 110 ^[1]	> 220 ^[1]
Absolute QRS Interval	msec	< 75 ^[1]	> 110 ^[1]

NOTES:

1. Represent standard ECG values of PCI for HIV studies.

10.7.3. Vital Signs

Vital Sign Parameter (Absolute)	Units	Clinical Concern Range	
		Lower	Upper
Systolic Blood Pressure	mmHg	< 85	> 160
Diastolic Blood Pressure	mmHg	< 45	> 100
Heart Rate	bpm	< 40	> 110

10.8. Appendix 8: Abbreviations & Trade Marks

10.8.1. Abbreviations

Abbreviation	Description
ADaM	Analysis Data Model
ADaM IG	Analysis Data Model Implementation Guide
AE	Adverse Event
AUC	Area under the concentration-time curve
AUC(0-t)	Area under the concentration-time curve from time 0 (predose) to time of the last quantifiable concentration
AUC(0-24)	Area under the concentration-time curve over time 0 (predose) to 24 hours after dose administration
AUC(0-72)	Area under the concentration-time curve over time 0 (predose) to 72 hours after dose administration
AUC(0-∞)	Area under the concentration-time curve from time 0 (predose) extrapolated to infinite time
%AUCex	The percentage of AUC(0-∞) obtained by extrapolation
BMI	Body Mass Index
C24	The observed concentration at 24 hours after dose administration
CDISC	Clinical Data Interchange Standards Consortium
CL/F	The apparent oral clearance
Cmax	Maximum observed concentration
CI	Confidence Interval
Ct	The last observed quantifiable concentration
CTMS	Clinical Trial Management System
CV	Coefficient of variation
CV _b	Coefficient of variation (Between)
DAIDS	Division of Acquired Immune Deficiency Syndrome
DTG	Dolutegravir
ECG	Electrocardiogram
eCRF	Electronic Case Report Form
GSK	GlaxoSmithKline
ICH	International Conference on Harmonisation
IDSL	Integrated Data Standards Library
kg	Kilograms
m	Meters
mg	Milligrams
msec	Milliseconds
PK	Pharmacokinetic
QTcF	Fridericia's QT Interval Corrected for Heart Rate
QTcB	Bazett's QT Interval Corrected for Heart Rate
R&D	Research and Development
RAP	Reporting & Analysis Plan
RPV	Rilpivirine
SAC	Statistical Analysis Complete

Abbreviation	Description
SAS	Statistical Analysis Software
SD	Standard deviation
SDTM	Study Data Tabulation Model
t	Time of last quantifiable concentration
TFL	Tables, Figures & Listings
t½	Terminal phase half-life
tlag	Lag time before observation of drug concentrations in sampled matrix
Tlast	Time of last quantifiable concentration
Tmax	Time to first occurrence of Cmax
Vz/F	The apparent volume of distribution during the terminal phase
λz	terminal phase rate constant

10.8.2. Trademarks

Trademarks of the GlaxoSmithKline Group of Companies	Trademarks not owned by the GlaxoSmithKline Group of Companies
JULUCA	DAIDS
TIVICAY	EDURANT

10.9. Appendix 9: List of Data Displays

10.9.1. Data Display Numbering

The following numbering will be applied for RAP generated displays:

Section	Tables	Figures
Study Population	1.1 to 1.7	N/A
Safety	3.1 to 3.13	N/A
Pharmacokinetic	4.1 to 4.6	4.1 to 4.10
Section	Listings	
ICH Listings	1 to 29	
Other Listings	30 to 33	

10.9.2. Deliverables

Delivery [Priority] ^[1]	Description
SAC [1]	Final Statistical Analysis Complete

NOTES:

1. Indicates priority (i.e. order) in which displays will be generated for the reporting effort

10.9.3. Study Population Tables

Study Population Tables					
No.	Population	IDSL / Example Shell	Title	Programming Notes	Deliverable [Priority]
Subject Disposition					
1.1.	Safety	ES1	Summary of Participant Disposition for the Participant Conclusion Record		SAC [1]
1.2.	Screened	ES6	Summary of Screening Status and Reasons for Screen Failure		SAC [1]
1.3.	Screened	DV1	Summary of Important Protocol Deviations		SAC [1]
1.4.	Safety	DM1	Summary of Demographic Characteristics		SAC [1]
1.5.	Enrolled	DM11	Summary of Age Ranges		SAC [1]
1.6.	Safety	DM5	Summary of Race and Racial Combinations		SAC [1]
Prior and Concomitant Medications					
1.7.	Safety	MH1 / MH4	Summary of Current Medical Conditions		SAC [1]

10.9.4. Safety Tables

Safety: Tables					
No.	Population	IDSL / Example Shell	Title	Programming Notes	Deliverable [Priority]
Adverse Events (AEs)					
3.1.	Safety	AE1	Summary of All Adverse Events by System Organ Class and Preferred Term		SAC [1]
3.2.	Safety	AE1	Summary All Drug-Related Adverse Events		SAC [1]
3.3.	Safety	AE5a	Summary of Adverse Events by Maximum Grade by System Organ Class and Preferred Term		SAC [1]
Laboratory: Chemistry					
3.4.	Safety	LB1	Summary of Chemistry Values		SAC [1]
3.5.	Safety	LB1	Summary of Chemistry Changes from Baseline	Add Footnote - Note: Baseline is defined as Day -1	SAC [1]
3.6.	Safety	LB16	Summary of Chemistry Results by Maximum Grade Increase Post-Baseline Relative to Baseline		SAC [1]
Laboratory: Hematology					
3.7.	Safety	LB1	Summary of Hematology Values		SAC [1]
3.8.	Safety	LB1	Summary of Hematology Changes from Baseline	Add Footnote - Note: Baseline is defined as Day -1	SAC [1]
3.9.	Safety	LB16	Summary of Hematology Results by Maximum Grade Increase Post-Baseline Relative to Baseline		SAC [1]

Safety: Tables					
No.	Population	IDSL / Example Shell	Title	Programming Notes	Deliverable [Priority]
Laboratory: Urinalysis					
3.10.	Safety	LB1	Summary of Urinalysis Dipstick Results		SAC [1]
Laboratory: ECG					
3.11.	Safety	EG1	Summary of ECG Findings		SAC [1]
Vital Signs					
3.12.	Safety	VS1	Summary of Vital Signs		SAC [1]
3.13.	Safety	VS1	Summary of Change from Baseline in Vital Signs	Add Footnote - Note: Baseline is defined as Day 1 (Predose)	SAC [1]

10.9.5. Pharmacokinetic Tables

Pharmacokinetic: Tables					
No.	Population	IDSL / Example Shell	Title	Programming Notes	Deliverable [Priority]
PK Concentration Data					
4.1.	PK	PKCT1	Summary of DTG Plasma Pharmacokinetic Concentration-Time Data by Treatment		SAC [1]
4.2.	PK	PKCT1	Summary of RPV Plasma Pharmacokinetic Concentration-Time Data by Treatment		SAC [1]
PK Derived Parameters					
4.3.	PK	PKPT1	Summary of Derived DTG Plasma Pharmacokinetic Parameters (Non-Transformed) by Treatment	Parameters with units	SAC [1]
4.4.	PK	PKPT3	Summary of Derived DTG Plasma Pharmacokinetic Parameters (Loge-transformed) by Treatment	Parameters with units	SAC [1]
4.5.	PK	PKPT1	Summary of Derived RPV Plasma Pharmacokinetic Parameters (Non-Transformed) by Treatment	Parameters with units	SAC [1]
4.6.	PK	PKPT3	Summary of Derived RPV Plasma Pharmacokinetic Parameters (Loge-transformed) by Treatment	Parameters with units	SAC [1]

10.9.6. Pharmacokinetic Figures

Pharmacokinetic: Figures					
No.	Population	IDSL / Example Shell	Title	Programming Notes	Deliverable [Priority]
Individual Concentration Plots					
4.1.	PK	PKCF1	Individual participant DTG Plasma Concentration-Time Plots by Participant (Linear and Semi-Logarithmic)	Paginate by Participant	SAC [1]
4.2.	PK	PKCF1	Individual participant RPV Plasma Concentration-Time Plots by Participant (Linear and Semi-Logarithmic)	Paginate by Participant	SAC [1]
4.3.	PK	PKCF6	Individual participant DTG Plasma Concentration-Time Plots by treatment (Linear and Semi-Logarithmic)	Only 1 page as one Treatment group	SAC [1]
4.4.	PK	PKCF6	Individual participant RPV Plasma Concentration-Time Plots by treatment (Linear and Semi-Logarithmic)	Only 1 page as one Treatment group	SAC [1]
Mean / Median Concentration Plots					
4.5.	PK	PKCF2	Arithmetic Mean DTG Plasma Concentration-time Plot (Linear and Semi-log)	Use nominal times in X Axis,	SAC [1]
4.6.	PK	PKCF2	Arithmetic Mean RPV Plasma Concentration-time Plot (Linear and Semi-log)	Use nominal times in X Axis,	SAC [1]
4.7.	PK	PKCF3	Median DTG Plasma Concentration-time Plot (Linear and Semi-log)	Use nominal times in X Axis,	SAC [1]
4.8.	PK	PKCF3	Median RPV Plasma Concentration-time Plot (Linear and Semi-log)	Use nominal times in X Axis,	SAC [1]

Pharmacokinetic: Figures					
No.	Population	IDSL / Example Shell	Title	Programming Notes	Deliverable [Priority]
PK Derived Parameters					
4.9	PK	Figure 3.19 201674	Individual and Box Plot of DTG PK Parameters by Treatment	AUC(0-∞), AUC(0-24), AUC(0-72), AUC(0-t), %AUCex, CL/F, C24, Cmax, t½, tlag, tlast, tmax, Vz/F	SAC [1]
4.10	PK	Figure 3.19 201674	Individual and Box Plot of RPV PK Parameters by Treatment	AUC(0-∞), AUC(0-24), AUC(0-72), AUC(0-t), %AUCex, CL/F, C24, Cmax, t½, tlag, tlast, tmax, Vz/F	SAC [1]

10.9.7. ICH Listings

ICH: Listings					
No.	Population	IDSL / Example Shell	Title	Programming Notes	Deliverable [Priority]
Subject Disposition					
1.	Screened	ES7	Listing of Reasons for Screen Failure		SAC [1]
2.	Safety	ES2	Listing of Reasons for Study Withdrawal		SAC [1]
3.	Safety	TA1 / CP_RD1x	Listing of Planned and Actual Treatments		SAC [1]
Protocol Deviations					
4.	Safety	DV2	Listing of Important Protocol Deviations		SAC [1]
5.	Safety	IE4	Listing of Participants with Inclusion/Exclusion Criteria Deviations		SAC [1]
Populations Analysed					
6.	Screening	SP3	Listing of Participants Excluded from Any Population		SAC [1]
Demography					
7.	Safety	DM4	Listing of Demographic Characteristics		SAC [1]
8.	Safety	DM10	Listing of Race		SAC [1]
Prior and Concomitant Medications					
9.	Safety	CP_CM4	Listing of Concomitant Medications		SAC [1]
Exposure					
10.	Safety	EX34	Listing of Exposure Data		SAC [1]
Adverse Events					
11.	Safety	CP_AE9	Listing of All Adverse Events		SAC [1]
12.	Safety	CP_AE9	Listing of Drug Related Adverse Events		SAC [1]

ICH: Listings					
No.	Population	IDSL / Example Shell	Title	Programming Notes	Deliverable [Priority]
13.	Safety	AE8	Listing of Non-Serious Adverse Events		SAC [1]
14.	Safety	AE7	Listing of Subject Numbers for Individual Adverse Events		SAC [1]
15.	Safety	AE2	Listing of Relationship Between Adverse Event System Organ Classes, Preferred Terms, and Verbatim Text		SAC [1]
Serious and Other Significant Adverse Events					
16.	Safety	CP_AE9	Listing of Adverse Events Leading to Withdrawal from study		SAC [1]
17.	Safety	CP_AE9a	Listing of Serious Adverse Events		SAC [1]
All Laboratory					
18.	Safety	LB6	Listing of Clinical Chemistry Toxicities of all Lab Abnormalities		SAC [1]
19.	Safety	LB6	Listing of All Clinical Chemistry Data for Participants with Lab Abnormalities		SAC [1]
20.	Safety	LB6	Listing of Hematology Toxicities of all Lab Abnormalities		SAC [1]
21.	Safety	LB6	Listing of All Hematology Data for Participants with Lab Abnormalities		SAC [1]
22.	Safety	LB6	Listing of Urinalysis Data for Subjects with Positive Dipstick or Microscopic Results		SAC [1]
ECG					
23.	Safety	EG4	Listing of All ECG Values for Participants with Any Value of Potential Clinical Importance		SAC [1]
24.			Listing of ECG Values of Potential Clinical Importance		
25.	Safety	EG6	Listing of All ECG Findings for Participants with an Abnormal ECG Finding		SAC [1]
26.	Safety	EG6	Listing of Abnormal ECG Findings		SAC [1]
Vital Signs					

ICH: Listings					
No.	Population	IDSL / Example Shell	Title	Programming Notes	Deliverable [Priority]
27.	Safety	VS5	Listing of All Vital Signs Data for Participants with Any Value of Potential Clinical Importance		SAC [1]
28.	Safety	VS5	Listing of Vital Signs of Potential Clinical Importance		
Liver Events					
29.	Safety	LIVER5	Listing of Liver Monitoring/Stopping Event Reporting		SAC[1]

